13.7. Appendix 4: Clinical Laboratory Tests

Table 13-7: Clinical Laboratory Tests

Safety Laboratory Assessments		Screening Tests for Eligibility^a	Immunogenicity Assessments
Clinical Chemistry 
 • Panel • Sodium • Potassium • Chloride • Bicarbonate • Total protein • Albumin • Calcium • Magnesium • Phosphorus • Glucose (random) • BUN • Creatinine • Cholesterol • Uric Acid • Total bilirubin • Direct (conjugated) bilirubin • Indirect (unconjugated) bilirubin • ALT • AST • Alkaline phosphatase • Creatinine kinase • GGT 	Hematology 
 • Red blood cells • Hemoglobin • Hematocrit • MCV, MCH, MCHC • Platelets • White blood cells • WBC Differential (% and absolute) • Neutrophils • Eosinophils • Basophils • Lymphocytes • Monocytes 	
 • Hepatitis B surface antigen • Hepatitis C antibody • HIV antibody • FSH (women only, as clinically warranted) • Serum/urine βhCG • Urine drug/alcohol screen • HbA1c (if warranted for individuals with diabetes mellitus, Type 2) 
Virology
 
 • SARS-CoV-2 detection by RT-PCR 	
 • SARS-CoV-2 neutralizing antibody titer by pseudoviral microneutralization assay [all participants] and optional PRNT assay [all/some participants] • [All participants] Anti-S, N-, and RBD protein IgG by MSD multiplex assay • [CMI subset only] Cytokine-producing SARS-CoV-2 spike protein-specific T-cells as measured by flow cytometry • [CMI subset only] ICS assay (Tumor necrosis factor (TNF)-α, Interleukin-2 (IL-2), Interferon-γ (IFN- γ), IL-4, and IL-13) • Additional exploratory immunogenicity tests will be specified in the SAP, if performed.

^a Can be performed at a local laboratory if the tests are available. Repeat safety laboratory testing (except toxicity screen and pregnancy test) at Screening will not be permitted unless the result is uninterpretable, or Screening assessments are repeated due to lapse of the 14-day screening visit window.

13.8. Appendix 5: FDA CBER Toxicity Grading Scales

Table 13-8: Toxicity Grading for Solicited Adverse Events

Solicited Local AEs	Grade 0 ⁺	Grade 1 (Mild)	Grade 2 (Moderate)	Grade 3 (Severe)	Grade 4 (Potentially Life Threatening)
Injection Site Erythema *	< 2.5 cm	2.5 – 5 cm	5.1 – 10 cm	> 10 cm	Necrosis or exfoliative dermatitis
Injection Site Induration/Swelling **	< 2.5 cm	2.5 – 5 cm and does not interfere with activity	5.1 – 10 cm or interferes with activity	>10 cm or prevents daily activity	Necrosis
Injection Site Pain	None	Does not interfere with activity	Repeated use of non-narcotic pain reliever > 24 hours or interferes with activity	Any use of narcotic pain reliever or prevents daily activity	Emergency room (ER) visit or hospitalization
Injection Site Tenderness	None	Mild discomfort to touch	Discomfort with movement	Significant discomfort at rest	ER visit or hospitalization
Solicited Systemic AEs					
Fever (°C) *** (°F) ***	<38.0 <100.4	38.0 – 38.4 100.4 – 101.1	38.5 – 38.9 101.2 – 102.0	39.0 – 40 102.1 – 104	>40 >104
Nausea/vomiting	None	No interference with activity or 1 – 2 episodes/24 hours	Some interference with activity or > 2 episodes/24 hours	Prevents daily activity, requires outpatient IV hydration	ER visit or hospitalization for hypotensive shock
Diarrhoea	None reported or 1 loose stool/24 hours	2 – 3 loose stools or < 400 gms/24 hours	4 – 5 stools or 400 – 800 gms/24 hours	6 or more watery stools or > 800 gms/ 24 hours or requires outpatient IV hydration	ER visit or hospitalization
Headache	None	No interference with activity	Repeated use of non- narcotic pain reliever > 24 hours or some interference with activity	Significant; any use of narcotic pain reliever or prevents daily activity	ER visit or hospitalization
Fatigue	None	No interference with activity	Some interference with activity	Significant; prevents daily activity	ER visit or hospitalization
Myalgia	None	No interference with activity	Some interference with activity	Significant; prevents daily activity	ER visit or hospitalization
Arthralgia, chills, dizziness	None	No interference with activity	Some interference with activity not requiring medical intervention	Prevents daily activity and requires medical intervention	ER visit or hospitalization

+ Grade 0 is defined as subject assessed with either no symptom or reported symptom less than Grade 1.

* In addition to grading the measured local reaction at the greatest single diameter, the measurement should be recorded as a continuous variable.

** Induration/Swelling should be evaluated and graded using the functional scale as well as the actual measurement.

*** Oral temperature; no recent hot or cold beverages or smoking.

Source: DHHS 2007

Table 13-9: Toxicity Grading for Safety Laboratory Assessments

Laboratory Parameter*	Mild (Grade 1)	Moderate (Grade 2)	Severe (Grade 3)	Potentially Life-Threatening (Grade 4)**
Sodium – Hyponatremia mEq/L	132 – 134	130 – 131	125 – 129	< 125
Sodium – Hypernatremia mEq/L	144 – 145	146 – 147	148 – 150	> 150
Potassium – Hyperkalemia mEq/L	5.1 – 5.2	5.3 – 5.4	5.5 – 5.6	> 5.6
Potassium – Hypokalemia mEq/L	3.5 – 3.6	3.3 – 3.4	3.1 – 3.2	< 3.1
Glucose – Hypoglycemia mg/dL	65 – 69	55 – 64	45 – 54	< 45
Glucose – Hyperglycemia Fasting – mg/dL Random – mg/dL	100 – 110 110 – 125	111 – 125 126 – 200	>125 >200	Insulin requirements or hyperosmolar coma
Blood Urea Nitrogen BUN mg/dL	23 – 26	27 – 31	> 31	Requires dialysis
Creatinine – mg/dL	1.5 – 1.7	1.8 – 2.0	2.1 – 2.5	> 2.5 or requires dialysis
Calcium – hypocalcemia mg/dL	8.0 – 8.4	7.5 – 7.9	7.0 – 7.4	< 7.0
Calcium – hypercalcemia mg/dL	10.5 – 11.0	11.1 – 11.5	11.6 – 12.0	> 12.0
Magnesium – hypomagnesemia mg/dL	1.3 – 1.5	1.1 – 1.2	0.9 – 1.0	< 0.9
Phosphorous – hypophosphatemia mg/dL	2.3 – 2.5	2.0 – 2.2	1.6 – 1.9	< 1.6
Creatinine kinase– mg/dL	1.25 – 1.5 x ULN***	1.6 – 3.0 x ULN	3.1 – 10 x ULN	> 10 x ULN
Albumin – Hypoalbuminemia g/dL	2.8 – 3.1	2.5 – 2.7	< 2.5	--
Total Protein – Hypoproteinemia g/dL	5.5 – 6.0	5.0 – 5.4	< 5.0	--
Liver Function Tests –ALT, AST increase by factor	1.1 – 2.5 x ULN	2.6 – 5.0 x ULN	5.1 – 10 x ULN	> 10 x ULN
Bilirubin – when accompanied by any increase in Liver Function Test increase by factor	1.1 – 1.25 x ULN	1.26 – 1.5 x ULN	1.51 – 1.75 x ULN	> 1.75 x ULN
Bilirubin – when Liver Function Test is normal; increase by factor	1.1 – 1.5 x ULN	1.6 – 2.0 x ULN	2.0 – 3.0 x ULN	> 3.0 x ULN
Hemoglobin (Female) - gm/dL	11.0 – 12.0	9.5 – 10.9	8.0 – 9.4	< 8.0
Hemoglobin (Female) change from baseline value - gm/dL	Any decrease – 1.5	1.6 – 2.0	2.1 – 5.0	> 5.0
Hemoglobin (Male) - gm/dL	12.5 – 13.5	10.5 – 12.4	8.5 – 10.4	< 8.5
Hemoglobin (Male) change from baseline value – gm/dL	Any decrease – 1.5	1.6 – 2.0	2.1 – 5.0	> 5.0
WBC Increase - cell/mm ³	10,800 – 15,000	15,001 – 20,000	20,001 – 25,000	> 25,000
WBC Decrease - cell/mm ³	2,500 – 3,500	1,500 – 2,499	1,000 – 1,499	< 1,000

Laboratory Parameter*	Mild (Grade 1)	Moderate (Grade 2)	Severe (Grade 3)	Potentially Life-Threatening (Grade 4)**
Lymphocytes Decrease - cell/mm ³	750 – 1,000	500 – 749	250 – 499	< 250
Neutrophils Decrease - cell/mm ³	1,500 – 2,000	1,000 – 1,499	500 – 999	< 500
Eosinophils - cell/mm ³	650 – 1500	1501 – 5000	> 5000	Hypereosinophilic
Platelets Decreased - cell/mm ³	125,000 – 140,000	100,000 – 124,000	25,000 – 99,000	< 25,000

* The laboratory values provided in the tables serve as guidelines and are dependent upon institutional normal parameters. Institutional normal reference ranges should be provided to demonstrate that they are appropriate.

** The clinical signs or symptoms associated with laboratory abnormalities might result in characterization of the laboratory abnormalities as Potentially Life Threatening (Grade 4). For example, a low sodium value that falls within a Grade 3 parameter (125-129 mEq/L) should be recorded as a grade 4 hyponatremia event if the subject had a new seizure associated with the low sodium value.

*** "ULN" is the upper limit of the normal range.

Source: DHHS 2007.

Toxicity Grading for Vital Signs

Vital Signs*	Grade 1 (Mild)	Grade 2 (Moderate)	Grade 3 (Severe)	Grade 4 (Potentially Life Threatening)
Tachycardia - beats per minute	101 – 115	116 – 130	> 130	ER visit or hospitalization for arrhythmia
Bradycardia - beats per minute***	50 – 54	45 – 49	< 45	ER visit or hospitalization for arrhythmia
Hypertension (systolic) – mm Hg	141 – 150	151 – 155	> 155	ER visit or hospitalization for malignant hypertension
Hypertension (diastolic) – mm Hg	91 – 95	96 – 100	> 100	ER visit or hospitalization for malignant hypertension
Hypotension (systolic) – mm Hg	85 – 89	80 – 84	< 80	ER visit or hospitalization for hypotensive shock
Respiratory Rate – breaths per minute	17 – 20	21 – 25	> 25	Intubation

* Subject should be at rest for all vital sign measurements.

*** When resting heart rate is between 60 – 100 beats per minute. Use clinical judgement when characterizing bradycardia among some healthy subject populations, for example, conditioned athletes.

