4.4.7. Reactogenicity Analysis Set

The Reactogenicity analysis set (RAS) includes all participants who receive any dose of priming study vaccine (ARCT-021 or placebo) and provide at least 1 reactogenicity diary report for the time period evaluated. Participants will be analyzed according to the vaccine received.

- Note: The RAS for re-enrolled participants consists of all re-enrolled participants who receive any dose of study vaccine while as a re-enrolled participant and provide at least 1 reactogenicity diary report for the time period evaluated.

The following analysis sets will be applicable for the Booster Vaccination Period:

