4.6. Missing Data Handling and Imputation Rules

No missing safety and reactogenicity results will be imputed. Incomplete AE onset and end dates will be imputed according to the rules specified in [Appendix 2](#). For safety analysis, percentages will be based on the analysis set of interest (e.g., Safety Set) within each treatment group and overall for the relevant vaccination/period of interest. For reactogenicity analysis, the denominator will be number of participants in the reactogenicity analysis set for the relevant vaccination/period of interest.

Any immunogenicity results that are below the limit of detection (LOD) or lower limit of quantification (LLOQ) will be imputed as half of the corresponding limit and results above the upper limit of quantification will be imputed as that limit for analysis purposes.

5. Participant Disposition and Protocol Deviations

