9.1.1. Reactogenicity

Any solicited local or systemic AE initiation within 7 days after each priming vaccination will be summarized by vaccination and by toxicity grade as number and percentage of participants. A summary by grade group (Grade 0 through 4 and Grade 1 through 4) will also be presented with 2-sided 95% CI using the Clopper-Pearson method. Grade 0 is a reported symptom lower than Grade 1. The duration of solicited local and systemic AEs after each vaccination will also be summarized. For injection site erythema, injection site induration/swelling, and diarrhea the duration for events graded 0 to 4 will be summarized. For all other solicited events, the duration for events graded 1 to 4 will be summarized.

Solicited local and systemic AEs through 7 days following each study vaccination will be evaluated by the participant and recorded in the diary as the following:

- Solicited local AEs: injection site erythema, injection site pain, injection site induration/swelling, injection site tenderness
- Solicited systemic AEs: arthralgia, chills, diarrhea, dizziness, fatigue, fever (categorized by measured body temperature), headache, myalgia, nausea/vomiting

Data will also be summarized by age group (≥ 18 to <56 years; ≥ 56 years).

The toxicity grade will be categorized by application of the DHHS CBER Toxicity Grading Scale. Participants will be counted once for the most severe event in cases where the participant reported more than one event per solicited AE category (e.g., pain).

For re-enrolled subjects and the booster vaccination period, summary of solicited AEs within 7 days post each vaccination by toxicity grade and age group will also be performed. In addition, a summary of solicited adverse events within 7 days post booster vaccination by grade and age group with active boosters pooled (as presented in Table 4-1; e.g., A1, A2, B1, B2, etc.) will be presented.

In addition, summary of solicited adverse events within 7 days post each priming vaccination by grade group and age group (≥ 18 to <65 years; ≥ 65 years) for Reactogenicity analysis set will be provided.

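### The SAP defines Grade 0 in two conflicting ways; if the Table 13-8 definition is applied, the planned Grade 0 to 4 reactogenicity summary is about 100% in every group, placebo included.

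*SAP*

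**What the plan says.** SAP 9.1.1 (Reactogenicity) plans the following: "A summary by grade group (Grade 0 through 4 and Grade 1 through 4) will also be presented with 2-sided 95% CI". The method is Clopper-Pearson. The sentence directly after it gives the meaning of the lowest grade: "Grade 0 is a reported symptom lower than Grade 1". On this reading a participant with no symptom has no grade.

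SAP 13.8 (Appendix 5), in the footnote to Table 13-8, gives another meaning: "Grade 0 is defined as subject assessed with either no symptom or reported symptom less than Grade 1". The Grade 0 column follows the footnote:

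- Pain, tenderness, nausea/vomiting, headache, fatigue, myalgia, arthralgia, chills and dizziness: none.
- Fever: any temperature below 38.0 °C.
- Diarrhoea: "None reported or 1 loose stool/24 hours".
- Erythema and induration/swelling: below 2.5 cm, which read literally includes 0 cm.

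Three other rules bear on the result. Under 9.1.1, "Participants will be counted once for the most severe event" within a solicited category. Under SAP 4.6, "the denominator will be number of participants in the reactogenicity analysis set for the relevant vaccination/period of interest", and "No missing safety and reactogenicity results will be imputed". Under SAP 4.4.7, members of that set must "provide at least 1 reactogenicity diary report for the time period evaluated".

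Protocol Table 13-4 has no Grade 0 column, so Grade 0 is an addition made in the SAP. SAP Section 11, which lists changes from the planned analysis, does not mention it.

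**The concern.** Section 9.1.1 also says that grades come from applying the DHHS CBER toxicity scale, and the SAP's version of that scale is in Appendix 5. Someone deriving the grade from that table would meet a definition that conflicts with the one in 9.1.1. Nothing in the SAP says which governs. The rule that the SAP prevails over the protocol does not help, because both statements are in the SAP.

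Reactogenicity against placebo is part of a primary objective (SAP 2.1). At stake is one of the two planned grade-group summaries, which 9.1.1 also calls for by age below 65 against 65 and over. Under the table's definition that summary would look like a result, with confidence intervals, yet could not distinguish vaccine from placebo.

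**Working it through.** The documents state no Grade 0 to 4 rate, so there is no planned figure to reproduce. The check is set logic, followed by the SAP's own interval method.

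**Notation.** For one vaccination and one treatment group, let n be the number in the reactogenicity set. Let A be those with no symptom, S those whose worst report is below Grade 1, and G those whose worst grade is 1 to 4. Each person is counted once at the worst grade, so with complete items A + S + G = n.

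**Table 13-8 definition.** Grade 0 covers A and S, so

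rate(0 to 4) = (A + S + G)/n = n/n = 100%.

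This holds in every group, and any between-group difference is 0 by construction.

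**Interval.** When all n participants count, the Clopper-Pearson lower limit is 0.025^(1/n) and the upper limit is 1. SAP 4.2 plans 75 per Study Group per age cohort, or 2 × 75 = 150 per Study Group.

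| n | Lower limit | 95% interval |
|---|---|---|
| 75 | 0.025^(1/75) = 0.952 | 95.2% to 100% |
| 150 | 0.025^(1/150) = 0.976 | 97.6% to 100% |

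**Missing items.** One diary report admits a participant to the set, and nothing is imputed. For a single symptom the rate can therefore fall short. With n=150 and 1, 3 or 5 members lacking the item, it is 149/150 = 99.3%, 147/150 = 98.0% or 145/150 = 96.7%. The shortfall measures diary completeness.

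**9.1.1 definition.** Grade 0 covers S only, so

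rate(0 to 4) = (S + G)/n,

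which can differ between groups. The documents give no placebo rate and no sub-threshold counts. The counts below are assumptions for illustration: n=150, with S=8 in each group. Protocol 1.5 reports that more than 90% of ARCT-021 recipients had a solicited event; 90% is used here.

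| Group (assumed) | Grade 1 to 4 | Grade 0 to 4, per 9.1.1 | Grade 0 to 4, per Table 13-8 |
|---|---|---|---|
| Placebo, low | 45/150 = 30% | 53/150 = 35.3% (27.7 to 43.5) | 100% |
| Placebo, middle | 75/150 = 50% | 83/150 = 55.3% (47.0 to 63.4) | 100% |
| Placebo, high | 105/150 = 70% | 113/150 = 75.3% (67.6 to 82.0) | 100% |
| ARCT-021 | 135/150 = 90% | 143/150 = 95.3% (90.6 to 98.1) | 100% |

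Over this range the vaccine-minus-placebo difference in the Grade 0 to 4 row is between 95.3 − 35.3 = 60.0 and 95.3 − 75.3 = 20.0 percentage points under 9.1.1. Under Table 13-8 it is 0. The Grade 1 to 4 column does not depend on the definition.

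**The case against.** The strongest reply is that 9.1.1 already settles the matter. The sentence planning the summary is followed at once by the narrower definition, and the section opens by limiting the summary to solicited events that begin within 7 days. A participant without symptoms has no such event. The protocol's version of the scale has no Grade 0, so the section that uses the term should govern. The documents contain no programming specification, so it is only an inference that the table would be applied. A row near 100% on placebo would also be conspicuous, and SAP Section 10 schedules a dry run of the safety outputs before final lock.

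Much of this stands. The 100% result is conditional, and exactly 100% for a single symptom also needs complete items. The reply does not remove the contradiction: the table's cells, and not only its footnote, count the symptom-free, and no text gives 9.1.1 precedence.

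Two stronger readings are tempting. A reader might infer that the durations would be diluted by participants without the event. The documents do not support this. Section 9.1.1 summarizes durations of events, using Grades 0 to 4 only for erythema, induration/swelling and diarrhea, the three symptoms with a possible reported state below Grade 1. That rule fits the reported-symptom meaning, and a person without an event has no event duration. A reader might also infer that the Grade 0 to 4 row should be dropped for the other symptoms. That is a preference: under 9.1.1, where Grade 0 can only mean none, the row simply equals the Grade 1 to 4 row. Fever is the exception, because its Grade 0 cell takes in every normal temperature, so it needs an explicit rule.

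**Conclusion.** The SAP is wrong as written on this point, as a minor internal inconsistency. If the Table 13-8 definition is applied, the Grade 0 to 4 summary is about 100% in every group, short of that only through missing diary items, and carries no reactogenicity information. If 9.1.1 is applied, the row is informative, mainly for erythema, induration/swelling and diarrhea.

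The conclusion rests on the reactogenicity-set denominator, the worst-grade counting rule and the absence of imputation, all of which the SAP states. The interval limits use planned group sizes. The main reactogenicity result, the Grade 1 to 4 rates, is unaffected, and no stated decision depends on the Grade 0 to 4 row.

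**What to change.** Use the 9.1.1 definition throughout the SAP:

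- Amend the Table 13-8 footnote and Grade 0 column so that no symptom is coded as none, outside the 0 to 4 group.
- Code any temperature below 38.0 °C as none.
- Keep Grade 0 for reported, non-zero findings below Grade 1: erythema or induration/swelling under 2.5 cm, and a single loose stool in 24 hours. This matches the existing duration rule.

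The cost is a footnote, one table column and the matching derivation wording. No change to data collection, models or the Grade 1 to 4 outputs is needed.
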